1.3 Efficacy Assessments

1.3.1 Wrinkle Severity Rating Scale (WSRS)

WSRS is a 5-grade validated photograph-based scale designed for quantifying facial folds. Scoring of fold severity is based on a visual assessment of the length and depth of the NLF at a certain time point, not in comparison to the Baseline or pre-treatment appearance, see Table 1-1. Each score in the WSRS is exemplified by a photograph of NLFs.

 GALDERMA	Title SAP, 43CH1508, Restylane Defyne NLF	Doc id MA-31549
---	--	--------------------

Table 1-1: Wrinkle Severity Rating Scale (WSRS)

Grade	Description
1	Absent: No visible fold; continuous skin line.
2	Mild: Shallow but visible fold with a slight indentation; minor facial feature. Implant is expected to produce a slight improvement in appearance.
3	Moderate: Moderately deep fold; clear facial feature visible at normal appearance but not when stretched. Excellent correction is expected from injectable implant.
4	Severe: Very long and deep fold; prominent facial feature; less than 2 mm visible fold when stretched. Significant improvement is expected from injectable implant.
5	Extreme: Extremely deep and long fold; detrimental to facial appearance; 2 to 4 mm V-shaped fold when stretched. Unlikely to have satisfactory correction with injectable implant alone.

The Blinded Evaluator will perform assessment of each NLF using the WSRS at Screening, Baseline, and each follow-up visit.

CCI

 GALDERMA	Title SAP, 43CH1508, Restylane Defyne NLF	Doc id MA-31549
--	--	----------------------------------

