1.4 Efficacy Endpoints

1.4.1 Primary efficacy endpoint

The primary efficacy endpoint is the response rate based on the WSRS score, as assessed by the Blinded Evaluator at 6 months after last treatment.

Response rate is defined as the percentage of subjects with at least one (≥ 1) grade improvement on the WSRS.

 GALDERMA	Title SAP, 43CH1508, Restylane Defyne NLF	Doc id MA-31549
---	--	--------------------

Effective date:

2017-02-13 08:27

Effective

CCI

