2.4 Efficacy Analysis

2.4.1 *Data sets analyzed*

All efficacy variables will be analyzed using the FAS population. The primary analysis will be repeated using the PP population. If it is deemed necessary, other analyses will be repeated using the PP population.

2.4.2 *Handling of missing data*

As the study design is intra-individual, in which the outcome of both treatments to be compared is available on each subject, it is expected that when a data is missing, it will be missing for both NLFs in most of the cases. A majority of the deviations from the protocol can be expected to affect both NLFs and evaluations of the same subject the same way.

 GALDERMA	Title SAP, 43CH1508, Restylane Defyne NLF	Doc id MA-31549
--	--	----------------------------------

Effective date: 2017-02-13 08:27

Effective

Version: 1.0

FAS analyses of WSRS scores in the primary analysis will use multiple imputation method (MI) as the primary method for imputing missing values. Rather than imputing each missing observation by a single value, this approach represents a random sample of the missing values, and therefore accounts for the prediction uncertainty of the unknown missing values. Last observation carried forward (LOCF) will be used as an alternative imputation method.

Safety and PP analyses will be presented based on observed cases, i.e., no imputation of missing values will be performed.

(i) Use of MI

The imputation using MI will assume a Missing Completely at Random (MAR) mechanism. The MI procedure of the SAS® system will be used to generate five sets of data with missing values imputed from observed data. It is expected that the pattern of missing data will be monotonic, with slight deviations being corrected by the Markov Chain Monte Carlo (MCMC) method of the MI procedure. Linear regression will be employed to model the missing WSRS score, with the following covariates included in the imputation model: treatment and non-missing data from earlier time points (Baseline, Week 2, and Month 3). The imputed datasets will be analyzed using the methodology described for the primary analysis of response rates at Month 6. The results from the analysis of the multiple imputed datasets will be presented as appropriate. The seed number to be used will be 431508.

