2.4.3 Primary analysis

Non-inferiority testing of Restylane Defyne relative to Restylane will be assessed on the 95% confidence interval approach with a non-inferiority margin of 15%. The confidence interval will be constructed for the difference (Restylane minus Restylane Defyne) in response rates at the 6 months follow-up visit (Table 8-1 and Table 8-2). Non-inferiority will be declared if the two-sided 95% interval is fully below 15%, i.e., the upper bound of the interval is less than 15% in both the FAS and PP populations.

To assess the robustness of the results using the MI method, LOCF will be used as an alternative imputation method. The same summary of primary analysis results will also be presented for observed cases (OC), (Table 8-1).

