4.3 Disposition of subjects

Table 4-4: Disposition of subjects: screened, treated, completed, and withdrawn subjects by site

Site	Screened subjects		Treated subjects		Completed subjects		Withdrawn subjects	
	n	%	n	%	n	%	n	%
Site 1								
Site 2								
Site 3								
Site 4								
Total (N)								

$\% = n/N*100$

Table 4-5: Subject accountability by visit

Visit	Expected subjects	Screening failures	Treated subjects	WSRS performed	Completed subjects	Withdrawn subjects
	n	n	n	n	n	n
Screening						
Baseline (Initial treatment)						
Week 4 follow-up / Optional touch-up treatment						
Week 4 follow-up after touch-up treatment						
Month 3 after last treatment						
Month 6 after last treatment						
Month 9 after last treatment						
Month 12 after last treatment						

$\% = n/N*100$

 GALDERMA	Title SAP, 43CH1508, Restylane Defyne NLF	Doc id MA-31549
--	--	--------------------

Table 4-6: Summary of screening failures

Site	Subject screening number	Date of screening	Reason for screening failure

Any extra comments here ...

[figure not shown]
Table 4-7: Withdrawn subjects

Site	Subject number	Date of treatment		Last visit performed	Date of withdrawal	Reason for withdrawal
		Initial treatment	Optional touch-up treatment			

Any extra comments here ...

 GALDERMA	Title SAP, 43CH1508, Restylane Defyne NLF	Doc id MA-31549
---	--	--------------------

Figure 4-1: Flowchart of study visits and subject accountability

 GALDERMA	Title SAP, 43CH1508, Restylane Defyne NLF	Doc id MA-31549
---	--	--------------------

5 Appendix B: Demographics

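### The primary FAS imputation treats a whole-grade score as continuous without saying how imputed values are turned into response, and it lists a Week 2 score that is never collected.

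*SAP*

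**What the plan says.** Protocol 10.6 makes multiple imputation the primary method for missing WSRS in the FAS but names no model or covariates. SAP 2.4.2(i) supplies them: "Linear regression will be employed to model the missing WSRS score", with "covariates included in the imputation model: treatment and non-missing data from earlier time points (Baseline, Week 2, and Month 3"). Five imputed datasets and a fixed seed are specified. Then: "The imputed datasets will be analyzed using the methodology described for the primary analysis of response rates at Month 6". The mechanism is labelled thus: "The imputation using MI will assume a Missing Completely at Random (MAR) mechanism".

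On visits, SAP 1.3.1 states: "The Blinded Evaluator will perform assessment of each NLF using the WSRS at Screening, Baseline, and each follow-up visit". SAP Table 4-5 has one Week 4 row for the visit after initial treatment and another, "Week 4 follow-up after touch-up treatment", but no Week 2 row.

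The endpoint in SAP 1.4.1 opens "Response rate is defined as the percentage of subjects with at least one" and continues with a grade of improvement on the 1-5 scale. SAP 2.4.3 declares non-inferiority only if "the upper bound of the interval is less than 15% in both the FAS and PP populations". Table 8-1 shows MI as the primary FAS row, with LOCF and observed cases beneath it as sensitivity rows. The PP analysis uses observed cases only.

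**The concern.** There are two gaps in one short paragraph.

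The main one is the imputation scale. WSRS takes whole grades, so observed improvement is 0, 1, 2 and so on. Linear-regression draws fall between grades. A draw of 0.8 grade of improvement is a non-responder if scored as it stands and a responder if rounded. The SAP does not say which applies, so a programmer would decide the primary FAS response rates, which are also reported separately in Table 8-3.

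The lesser one is the covariate list. Week 2 cannot be supplied from the data. Reading it as Week 4 does not settle the model, because touched-up subjects have two Week 4 scores. The first precedes their last treatment, whereas Months 3 and 6 are counted from the last treatment.

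Both gaps sit in one of the two analyses that must pass, and the fixed seed shows that a reproducible result was intended.

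**Working it through.** **1. Visit check.** WSRS rating times in the protocol (synopsis visit list, 4.1, Table 1, 7.2) and SAP Table 4-5 are screening, baseline, Week 4 after initial treatment, Week 4 after touch-up (touched-up subjects only), and Months 3, 6, 9 and 12. None is Week 2. The WSRS row and visit columns are legible, so redaction does not explain the absence. SAP 2.8, in its visible text, does not mention it.

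**2. Inputs.** From the documents: about 175 split-face subjects, a 15-point margin, a two-sided 95% interval and five imputations. Assumed, because the documents give no missing rate and the sample-size text is redacted: the missing fraction f, the response rates, and the share of responders improving two grades. There is no figure in the plan to reproduce.

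**3. Closed form.** Let improvement be 0, 1 or 2 grades with P(1) = p1 and P(2) = p2. Then mean m = p1 + 2·p2, SD s = √(p1 + 4·p2 − m²), and true response is p1 + p2. As an approximation that ignores covariates, a normal draw counts as response with probability Φ((m − 1)/s) if unrounded and Φ((m − 0.5)/s) if rounded to the nearest grade.

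| True response | p1, p2 | m | s | Unrounded | Rounded |
|---|---|---|---|---|---|
| 75% | .55, .20 | 0.950 | 0.669 | 47.0% | 74.9% |
| 65% | .468, .182 | 0.832 | 0.710 | 40.6% | 68.0% |
| 80% | .576, .224 | 1.024 | 0.651 | 51.5% | 79.0% |

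The last two rows assume that 28% of responders improve two grades.

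**4. Effect on each rate.** The error is f × (true − imputed). For 65% and 80% unrounded, it is 0.05 × 24.4 = 1.2 and 0.05 × 28.5 = 1.4 points at 5% missing, and 2.4 and 2.9 at 10%. Simulations with 175 subjects, five Bayesian linear-regression imputations, Rubin pooling and a paired Wald interval gave 1.2-1.5 points at 5%, 2.5-2.9 at 10% and about 5-6 at 20%. Varying response over 60-85% and two-grade responders over 15-40% of responders gave 0.9-1.8 points at 5% and 1.8-3.8 at 10%.

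**5. Effect on the decision.** Leaving draws unrounded raised the upper bound by 0.2 point at 5% missing, 0.3-0.4 at 10% and 0.7-0.8 at 20%. Power of the FAS-and-PP rule at no true difference, unrounded against rounded, was 95.2 vs 95.6%, 92.8 vs 93.8% and 87.2 vs 90.3%. A separate FAS-only simulation (1,000 runs per setting) with Restylane Defyne 0.1 grade worse gave 75.5 vs 80.3% at 10% missing and 66.9 vs 74.9% at 20%.

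**6. What rounding does not repair.** In the table, a true 15-point difference becomes 51.5 − 40.6 ≈ 10.8 points among unrounded imputed values (from unrounded inputs) and 79.0 − 68.0 = 11.0 among rounded ones. At 10% missing the overall difference shrinks by about 0.1 × 4 = 0.4 point either way, and at 20% by about 0.8. Simulation put the 20% figure at 0.8-0.9 in one model and, for rounded scores, 1.1 in another. Logistic imputation of response removed the shrinkage.

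**7. Which Week 4 score.** Using the initial rather than the last Week 4 score changed the two-population verdict in 0.5-1.0% of runs at a 15-point deficit. Rerunning the same model with new draws changed it in 0.4-0.9%.

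**8. False non-inferiority at a 15-point deficit, both populations required.** 0.012-0.025 with either Week 4 score and 0.014-0.030 with none. The complete-data interval alone gave 0.024-0.030.

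**The case against.** The strongest reply is that little depends on this. Week 2 looks like a slip, Baseline and Month 3 remain usable, and the governing idea of conditioning on earlier non-missing scores is clear. LOCF and observed-case results stand beside the MI row and do not use the imputation model. PP has no imputed scores and must also pass, so a faulty MI model alone cannot produce a non-inferiority claim. Unrounded scoring makes the claim harder to reach. All of this stands, and it limits the weight of the point.

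It is also fair that silence about rounding is not an instruction to score raw fractional values. A reader might infer that the SAP directs this, but the text only leaves it open. The understated rates follow under one of the two readings.

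Rounding is also not a complete answer. It is nearly exact at 75% response, but in the same approximation it overstates imputed response by 3.0 points at 65%, and by 6.8 at 60% with 40% two-grade responders (about 0.7 point overall at 10% missing). That stands, and it is why rounding is only the minimum remedy below.

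What the reply does not remove is that the derivation of response in the primary FAS row is undefined, and that LOCF and observed cases are labelled sensitivity analyses, not substitutes for it.

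**Conclusion.** The point holds as a specification defect that should be fixed. Its core is the imputation scale: if draws are scored as they come, each product's FAS response rate is understated by about 1.2-1.5 points at 5% missing and 2.5-2.9 at 10%, with a small loss of power at no true difference. The Week 2 entry is a correction with no demonstrated effect on the verdict. The sizes depend on assumed missing rates, response rates and correlations, and on a paired Wald interval.

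Two stronger readings are tempting. One is that the non-inferiority conclusion is at risk. The error largely cancels in the paired difference, and the simulated false-claim rates do not exceed those of the complete-data interval. Because both populations must pass, the false-claim rate also cannot exceed that of the imputation-free PP analysis. The shrinkage of a true difference does run towards non-inferiority, but no type I error inflation was found. The other is that the protocol dictates which Week 4 score to use. Its synopsis labels both visits Week 4, one at Day 29 and one after last treatment, so the choice is open.

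**What to change.** Amend SAP 2.4.2(i) before database lock.

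(a) Impute Month 6 responder status by logistic regression, or WSRS by cumulative logit, with a stated fallback if the data are too sparse to fit the model. This corrects both the rates and the shrinkage. At minimum, keep linear regression and add: *imputed scores are rounded to the nearest grade and limited to 1-5 before response is derived*. In that case acknowledge that the shrinkage remains, at about 0.4 point of a 15-point difference with 10% missing.

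(b) Replace Week 2 with a named, collected score. One option is Week 4 after last treatment: the visit after touch-up for touched-up subjects, and the visit after initial treatment for all others. State it as a choice that makes the model executable and reproducible. In simulation neither score was uniformly better. If dropout follows the last Week 4 score, the Restylane Defyne rate is 0.3 point high with that score and 0.5 with the initial one. If dropout follows the initial score, the figures are 0.6 and 0.1.

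(c) Change the label to *Missing at Random (MAR)*.

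The cost is a few lines of text, slightly more programming and, for logistic imputation, a slightly wider interval than rounding gives. No new data or visits are needed.

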4.7 Schedule of events

Table 1. Schedule of events

Activity	Screening ^a	Baseline ^a Initial treatment	Week 4 follow-up after Initial treatment/ Optional Touch-up treatment ^b	Week 4 follow-up after touch-up (for subjects who received touch-up)	Month 3, 6 and 9 follow-up	Month 12 follow-up / Final visit /Early termination
	Day -21 to 1	Day 1	Day 29 4 weeks (± 3 days) after initial treatment	4 weeks (± 3 days) after touch-up	3, 6 months (± 7 days) and 9 months (± 2 weeks) after last treatment ^c	12 months (± 2 weeks) after last treatment ^c
Informed consent	X					
Demography	X					
Medical history & concurrent diseases	X	X				
Concomitant medication/procedures	X	X	X	X	X	X
Vital signs		X				
Hematology	X					
Serum chemistry + Pregnancy Tests (S-HCG)	X					X
ECG	X					
Pregnancy test (U-HCG)		X ^{d,e}	X ^{d,e}			
Inclusion and Exclusion criteria	X	X				
Randomization		X				
Photography		X ^f	X ^f	X	X	X
Treatment		X	X ^b			
CCI						
WSRS (blinded evaluator)	X	X ^g	X ^e	X	X	X

	Title 43CH1508 Clinical Study Protocol	Doc id MA-29708
--	---	----------------------------------

Activity	Screening^a	Baseline^a Initial treatment	Week 4 follow-up after Initial treatment/ Optional Touch-up treatment^b	Week 4 follow-up after touch-up (for subjects who received touch-up)	Month 3, 6 and 9 follow-up	Month 12 follow-up / Final visit /Early termination
	Day -21 to 1	Day 1	Day 29 4 weeks (\pm 3 days) after initial treatment	4 weeks (\pm 3 days) after touch-up	3, 6 months (\pm 7 days) and 9 months (\pm 2 weeks) after last treatment ^c	12 months (\pm 2 weeks) after last treatment ^c
CCI						
Device deficiencies		X	X ^h			
CCI						
Assessment of Adverse Events		X	X	X	X	X
Study termination						X

- a) Screening visit and baseline visit can be combined to one visit, if feasible.
- b) Touch-up treatment may be performed for subjects who did not improve ≥ 1 grade in WSRS (in one or both NLFs, as assessed by the blinded evaluator). Touch-up treatment will not be performed without the subject's verbal consent, if there are ongoing treatment-related AEs or if optimal aesthetic improvement of both NLFs is already achieved.
- c) Last treatment is either the initial treatment or the touch-up treatment.

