4.8.6 Month 12 (± 2 weeks) follow-up/ Final visit or Early termination

A final follow-up visit will be performed 12 months ± 2 weeks after the last treatment visit. In the case of subject withdrawal between regular visits (Section 5.5) the subject should, when possible, be scheduled for an early termination visit.

Standardized photographs will be taken. WSRS will be completed by the blinded evaluator
CCI

. Any AEs since last visit or change in medications used will be reported. A final pregnancy test (U-HCG) will be performed in women of childbearing potential.

- Perform serum pregnancy test for all women of childbearing potential
- Laboratory assessments (serum chemistry)
- Assess WSRS (by blinded evaluator)
- Obtain photographs
CCI

- Interview for concomitant medications and treatments
- Interview for AE

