If withdrawal of a subject occurs between regular study visits the subject should, when possible (irrespective of the reason for withdrawal), be scheduled for a termination visit. In these cases the eCRF for early termination visit should be completed.

If a subject is withdrawn from the study, all data collected until the time of withdrawal will be used in the analyses.

A withdrawn or discontinued subject must not be replaced or re-entered into the study.

If an AE which, according to the Investigator's assessment, is related to the use of any of the study products and is still ongoing at the time of the withdrawal please refer to Section [8.4.6](#).

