11 PROTECTION OF PERSONAL DATA

The study shall follow the requirements as specified in People's Republic of China (PRC) Provisions for Clinical Trials of Medical Devices with respect to the processing and protection of personal data. For the purposes of the study, Sponsor will be considered the data controller, and the Institution and PI will both be considered data processors.

All processing of personal data and photos must be carried out in accordance with national legislation concerning the protection of personal data and photos. The Institution and the PI are responsible for complying with all requirements pursuant to national legislation in the country in which the Institution and the PI are located. The Sponsor will ensure that all

 GALDERMA	Title 43CH1508 Clinical Study Protocol	Doc id MA-29708
--	---	----------------------------------

Effective date: 2017-07-05 06:37

Effective

Version: 5.0

requirements are complied with for data processing, which is carried out in Sweden by the Sponsor.

The informed consent form shall contain information about what personal data and photos to be collected in the study and that this will be kept confidential. The provided information shall be sufficient to enable all subjects to give their consent not only to the participation in the study, but also to the processing of personal data and photos. Such information includes information regarding the purposes of the collection, processing, data transfer to countries outside China, and the length of time during which personal data will be stored. The subject shall have the right of access to stored personal data, and the right to correction of incorrect information. If a subject decides to discontinue the study prematurely, data collected before withdraw of consent will be used in the evaluation of the study, however no new data may be collected. Authorized representatives from the Sponsor, clinical research organization (CRO) or a RA may visit the study site to perform audits/inspections, including source data verification, i.e., comparing data in the subjects' medical records and the eCRF. Data and information shall be handled strictly confidential.

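### The primary imputation of a missing Month 6 WSRS stops at Month 3, so it leaves out the early-termination, Month 9 and Month 12 scores that the trial collects, and it names a Week 2 visit that does not exist

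*SAP*

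**What the plan says.** SAP 2.4.2(i) specifies five imputations. "Linear regression will be employed to model the missing WSRS score", and the covariates are "treatment and non-missing data from earlier time points (Baseline, Week 2, and Month 3"). An MCMC step is planned for departures from a monotone missing-data pattern. The stated mechanism is internally inconsistent, since the name and the abbreviation differ: "The imputation using MI will assume a Missing Completely at Random (MAR) mechanism". LOCF and observed cases are sensitivity analyses (SAP 2.4.3, Table 8-1).

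The protocol collects more than this list uses. For a withdrawal between regular visits, "the subject should, when possible, be scheduled for an early termination visit" (Protocol 4.8.6). At that visit "WSRS will be completed by the blinded evaluator". In the schedule of events (Protocol 4.7, Table 1), WSRS is marked in the column headed "Month 12 follow-up / Final visit /Early termination" and in the column for Months 3, 6 and 9. Protocol 5.5 adds: "If a subject is withdrawn from the study, all data collected until the time of withdrawal will be used in the analyses".

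There is a limit. Once consent is withdrawn, Protocol 11 says that "data collected before withdraw of consent will be used in the evaluation of the study, however no new data may be collected".

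The readable SAP has no rule assigning a termination score to a visit. Table 4-5 has no row for it, and the readable part of SAP 2.8 lists no change on this point.

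**The concern.** Multiple imputation under missing at random is only as credible as the observed predictors it conditions on. Two kinds of observed score bear directly on a missing Month 6 value and are not in the list:

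- **Early-termination WSRS.** If a subject leaves between Months 3 and 6, this is the observation closest to Month 6. A fold seen to have relapsed at termination is imputed from its Month 3 score.
- **Month 9 and Month 12 WSRS.** A subject who misses only Month 6 has later scores for the same fold. The list stops at Month 3.

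The list also names a Week 2 visit that the schedule lacks. Read literally, the usable covariates shrink to treatment, Baseline and Month 3.

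At stake is the primary result on the full analysis set, one of the two that must both show non-inferiority. The per-protocol analysis cannot reveal the problem, because it requires a completed Month 6 visit.

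**Working it through.** The plan states no figure on this point to reproduce, and the sample-size section is redacted. From the documents: about 175 subjects, each with both products; margin 15 points on Restylane minus Defyne; response is an improvement of at least one grade. Dropout, relapse and correlations over time are assumptions below.

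**1. How informative a termination score is.** Assume a latent improvement with means 1.2, 1.0 and 0.95 grades at Months 3, 5 and 6, SD 0.6, correlation r per month of separation, and response if the latent value is at least 0.5.

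| r | P(response M6, given response M3) | same, with non-response at a Month 5 termination | gap |
|---|---|---|---|
| 0.80 | 0.82 | 0.34 | 0.47 |
| 0.90 | 0.84 | 0.26 | 0.58 |
| 0.95 | 0.86 | 0.20 | 0.66 |

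At r = 0.9, one such fold is over-credited by 0.58 of a subject: 0.58/175 = 0.33 points of that product's response rate. Five subjects who all relapse on the same product, on one side only, give 5 × 0.58/175 = 1.7 points.

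**2. Arithmetic ceiling on the difference.** If k subjects are affected and all relapse on the Defyne side only, the shift is k/175: 2.9 points for k = 5, 5.1 for k = 9, 10.3 for k = 18.

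**3. Simulation of the listed model.** 600 replicates per scenario, N = 175 split-face, five imputations by linear regression on treatment, Baseline and Month 3, rounded to a grade. Assumed: 88% responders at Month 3, 88% of these retained at Month 6 in completers, and relapse seen at termination persisting to Month 6. Differences are Restylane minus Defyne, in points.

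| Subjects affected | Relapse Defyne / Restylane | Difference with relapse counted | Difference under the listed model | Shift |
|---|---|---|---|---|
| 3% | 60% / 30% | 0.67 | -0.15 | 0.8 |
| 5% | 60% / 30% | 1.53 | 0.21 | 1.3 |
| 10% | 60% / 30% | 2.45 | -0.25 | 2.7 |
| 3% | 90% / 30% | 1.83 | 0.26 | 1.6 |
| 5% | 90% / 30% | 2.61 | -0.01 | 2.6 |
| 10% | 90% / 30% | 5.24 | -0.10 | 5.3 |
| 5% | 60% / 60% | 0.29 | 0.26 | 0.0 |

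The equal-relapse row would be zero without simulation noise, so the shift column is the one to read. With equal relapse the difference is essentially unbiased, but both response rates are overstated: by about 1.3 points at 3% affected, 2.2 at 5% and 4.3 at 10%. Exchanging the two relapse rates reverses the sign of the shift.

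**4. What Month 9 adds when only Month 6 is missing.** With correlation r per month, the unexplained share of Month 6 variance is 1 − r⁶ given Month 3 alone, and (1 − r⁶)/(1 + r⁶) given Months 3 and 9. The reduction is r⁶/(1 + r⁶):

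- r = 0.80: 0.262/1.262 = 21%
- r = 0.95: 0.735/1.735 = 42%

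Under this correlation structure Month 12 adds nothing once Month 9 is known, but it helps when Month 9 is missing too.

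**The case against.** The strongest counter-case has five parts.

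- **The SAP is silent, not exclusionary.** It never says that a termination score is discarded. That is so, but the covariate list is explicit, and followed as written it gives the score no route into the primary result.
- **There is no clear breach of the protocol.** A reader might infer that the SAP contradicts Protocol 5.5. The documents do not support that firmly. The sentence covers data up to withdrawal, while a termination visit is arranged around or after it and only when possible. Use in the analyses also need not mean use in the primary imputation model. This objection stands.
- **LOCF covers it.** A termination score is a natural last observation, but the SAP does not say so, and LOCF is a sensitivity analysis only.
- **Both folds are usually missing together** (SAP 2.4.2). This limits the effect on the difference. It does not remove it, because each fold is scored separately and joint missingness does not imply equal relapse.
- **Few subjects are affected.** The SAP expects a mostly monotone pattern, so subjects missing only Month 6 should be few, and termination visits will not always take place. This stands as a limit on size, not as a reason to leave out scores that exist.

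**Conclusion.** The point holds as a weakness in the primary imputation that is cheap to correct. The covariate list omits observed scores that predict Month 6, and it names a visit that does not exist.

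A reader might infer that the omission favours Defyne. The documents do not support this. The bias favours non-inferiority only if the Defyne fold relapses more among the affected subjects, it works against non-inferiority if the Restylane fold does, and nothing in the documents predicts either. Nor do the 1.7 points amount to an estimate for this trial: they need five one-sided relapses, all on the same product, each with an attended termination visit.

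The size is unknown. On the assumptions shown, the shift in the difference runs from about zero with equal relapse to 5.3 points with 10% of subjects affected and 90% against 30% relapse. At low dropout it is probably small against the 15-point margin. These shifts assume that relapse seen at termination persists to Month 6.

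**What to change.** Amend SAP 2.4.2 before database lock:

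1. Count an early-termination WSRS as the observed Month 6 score in the full analysis set if it falls inside the SAP's Month 6 window (Table 2-1: 1 week before to 2 weeks after the scheduled visit).
2. Include the Month 9 and Month 12 WSRS of the same fold in the imputation model, through the MCMC step already planned.
3. For a termination score between Month 3 and that window, do not add a separate covariate. Its relation to Month 6 cannot be estimated, because the two are not both observed in one subject. State instead that LOCF uses it as the last observation.
4. Replace Week 2 with the Week 4 visit, and say which of the two Week 4 visits applies after a touch-up.

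Item 3 leaves the primary result unchanged for those subjects. It makes the effect visible by comparing LOCF with the primary result.

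The cost is SAP wording and a slightly larger imputation model. No new data are needed.
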